## 7. PARTICIPANT POPULATION

---

### a. Planned Enrollment

The number of participate expected to be enrolled at Stanford Medicine Fertility and Reproductive Health Clinic is 100 patients per patient population (100 recurrent pregnancy loss patients, 100 unexplained infertility patients and 100 health controls). Any patients eligible for the study but desiring no intervention will be offered the alternative of being included as an observational group only without intervention in order to compare pregnancy outcomes without intervention. These patients will be recurrent pregnancy loss and unexplained infertility patients seeking treatment at our facility. healthy controls will be patients presenting for elective egg freezing and sex selection.

---

### b. Age, Gender, and Ethnic Background

All participants enrolled in this study will be female and of reproductive age 18-45 years old that present to our clinic for routine evaluation and treatment. Enrollment will be open to women of all ethnic backgrounds.

---

### c. Vulnerable Populations

N/A

---

### d. Rationale for Exclusion of Certain Populations

Children will not be included as recurrent pregnancy loss and infertility does not occur in children.

---

### e. Stanford Populations

None

---

**f. Healthy Volunteers**

None

---

**g. Recruitment Details**

The participants will be recruited by their treating physician if they meet the inclusion criteria for the study. The study be open to the public and women who are already presenting to Stanford Medicine Fertility and Reproductive Health clinic will be invited to participate. Participants will be treated the same whether or not they agree to enrollment in the study. Those consenting to study participation will be willing to allow physician follow up for up to 5 years for thorough data collection.

---

**h. Eligibility Criteria**

i. Inclusion Criteria

Subjects must fulfill the following inclusion criteria to be eligible to participate in the study:

1. Have a diagnosis of recurrent pregnancy loss as defined as two or more unexplained pregnancy losses at less than 10 weeks (miscarriages with known chromosomal errors excluded) OR have a diagnosis of unexplained infertility defined as normal ovarian reserve testing, normal ovulatory function, normal semen analysis defined why WHO criteria and evidence of at least one patent fallopian tube.
2. Agree to the standard of care testing for evaluation of recurrent pregnancy loss OR unexplained infertility OR routine testing for preparation for oocyte freezing or elective sex selection.
3. Be at least 18 years old and less than 46 years old.
4. Have menstrual cycles that occur in 25-35 day intervals
5. Agree to follow up for 5 years from the date of enrollment

ii. Exclusion Criteria

1. Irregular menstrual cycles
2. Presence of untreated submucosal fibroids or polyps
3. an unligated hydrosalpinx
4. non-ovulatory progesterone level on the day of endometrial biopsy
5. Women <21 or >45 years old.

---

**i. Screening Procedures**

Study staff will invite women presenting for recurrent pregnancy loss or unexplained infertility or healthy controls to participate in this study. The staff will explain the purpose of the study to interested patients and the patients will then sign an informed consent for their enrollment. Patients will receive a thorough evaluation of their condition upon presentation. It will be emphasized that their participation is entirely voluntary and that they will receive the standard of care even if they choose not to enroll in the study or discontinue participation at any time.

---

**j. Participation in Multiple Protocols**

Patients will be asked if they are participating in any other studies on their consent forms. They may be enrolled in other studies concurrently with this study as long as it does not impact the outcome of this study.

---

**k. Payments to Participants**

No payment will be provided. Patients are receiving standard of care evaluation and management of recurrent pregnancy loss and unexplained infertility.

---

**l. Costs to Participants**

Standard recurrent pregnancy loss and unexplained infertility evaluation and treatment costs will be charged to the patient or her insurance. Similarly standard evaluation prior to oocyte freezing or sex selection cycles will be charted to the patient or her insurance.

---

**m. Planned Duration of the Study**

The probable duration of the study will be approximately 3-5 years to complete the patient's treatment of recurrent pregnancy loss and unexplained infertility and follow up the outcome of their pregnancies (if applicable) for up to 5 years.

---

**8. RISKS**

---

**a. Potential Risks**

i. Investigational devices

The ERA and microbiome tests pose no risks or injury to the subject. Participants will receive standard of care at the study site which includes an endometrial biopsy. A portion of this specimen will be sent free of charge for the endometrial receptivity array and microbiome evaluation.

ii. Investigational drugs

N/A

iii. Commercially available drugs, biologics, reagents or chemicals

Vaginal progesterone supplementation is often used empirically as an available treatment for patients with recurrent pregnancy loss. This will be offered to all patients who desire this empirical treatment if their ERA shows a non-receptive endometrium. These patients will be offered a repeat ERA biopsy to determine whether progesterone improves their endometrial receptivity.

Vaginal progesterone risks are considered minimal but patient's have reported in clinical trials to report symptoms such as abdominal pain (12%) nausea (8%) abdominal bloating (4%), constipation (2-3%) vomiting (3%), fatigue (2%), UTIs (2%) headache 4%, vaginal bleeding of 3%. Vaginal progesterone may also have similar side effects compared to other drugs containing progesterone including breast tenderness, bloating, mood swings, irritability, and drowsiness. If patients experience bothersome side effects that are not easily treated (for example a headache that resolves with a dose of Tylenol) we would stop vaginal progesterone treatment as is our current clinical practice.

Oral doxycycline is considered minimal risk but patients have reported in clinical trials to report symptoms such as nausea, decreased appetite, vomiting, diarrhea, hives and anemia. If these symptoms developed and didn't resolve with minimal intervention (taking food with medicine) the treatment would be stopped as is our current clinical practice.

iv. Procedures

Minimal risk to patients with non-invasive procedures. Patients will only receive standard of care diagnostic testing during their duration of treatment in our office. This will include ultrasounds, blood tests and a uterine cavity evaluation. A patient may experience mild discomfort at the venipuncture site and some lower abdominal cramping and light bleeding (spotting) associated with a uterine cavity evaluation. There are extremely low risks of infection or other complications associated with these minimally invasive procedures.

v. Radioisotopes/radiation-producing machines

N/A

vi. Physical well-being

Minimal risks to a patient's physical well-being. Patients are receiving standard medical treatment. Repeat biopsies will be offered to patients whose initial testing is not receptive. The risk of the repeat biopsy is again minimal physical risk and patients will be allowed to decline the repeat testing.

vii. Psychological well-being

Minimal risks to a patient's psychological well-being. Potential improvement to psychological well-being as the information from the ERA may help explain a previously unexplained diagnosis of recurrent pregnancy loss or unexplained infertility.

viii. Economic well-being

Participants will not be responsible for any costs associated with this study. They are receiving standard medical care and if they agree to the endometrial biopsy, the ERA and microbiome testing will be done for no additional cost.

ix. Social well-being

x. Participation in this study should not effect a patient's social well-being. Overall evaluation of risk

Low

---

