For patients whose ERA shows a non receptive endometrium in the subsequent menstrual cycle, vaginal progesterone medication which is often prescribed empirically for recurrent pregnancy loss will be prescribed to start 3 days after ovulation detected by home urine LH kits. A second endometrial biopsy will be sent for a repeat ERA at not

extra cost to the patient. The patient will still be able to participate in the study if they decline this second biopsy.

For patients who microbiome is altered, a 2 week course of oral doxycycline will be prescribed followed by 2 weeks of over the counter vaginal probiotics. A second endometrial biopsy will be sent for a repeat microbiome at not extra cost to the patient. The patient will still be able to participate in the study if they decline this second biopsy.

If on the first biopsy there is endometritis the patient will first be treated based on standard of care practice with routine use of oral antibiotics prior to undergoing a second endometrial biopsy which is also routine practice. If the microbiome or ERA is also abnormal (It would be for example EXPECTED that the microbiome will be altered in all endometritis patients) for an abnormal ERA- vaginal progesterone would be added prior to rebiopsy and/or vaginal probiotics would be added.

The patients' follow up visits and treatment regimens will be determined by the treating physician according to the standard of care treatment of recurrent pregnancy loss, unexplained infertility or other medical comorbidities.

These patients are not required to consent to any additional testing or drug treatments outside of that which is standard treatment of their condition(s). They will consent to follow up communication (phone call or email) for up to 5 years after enrollment in the study to allow for completion of data collection and pregnancy outcomes except for the healthy controls who will be followed for 1 year.

The only procedures which would be considered entirely research would be sending the endometrial biopsy tissue for ERA testing (currently endometrial biopsy is a standard of care for recurrent pregnancy loss and unexplained infertility) however this is not sent for ERA testing.

Empiric use of vaginal progesterone is often used in the setting of recurrent pregnancy loss and unexplained fertility however doing a repeat biopsy in this setting would be considered research- not standard of care.

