Use of antibiotics is often used in the setting of non-specific findings for endometritis in recurrent pregnancy and unexplained fertility however using this in the setting of an abnormal microbiome in combination with over the counter vaginal probiotics would be considered research.

---

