**e. Data Safety Monitoring Plan (DSMC)**

i. Data and/or events subject to review

Since we will be performing endometrial biopsies in patients enrolled in this study, there is a small risk of bleeding and infection that can occur as result of this intervention (<1%) We will keep track of all patients that experience complications as a result of this procedure.

For patients who use vaginal progesterone there is a small risk of side effects from systemic absorption of the progesterone: Bloating, stomach/abdominal pain, nausea, breast tenderness, headache, drowsiness, mood swings, irritability, or vaginal discomfort. In our experience we have found that <1% of our patients have bothersome side effects with vaginal progesterone which we routinely use for many infertility and recurrent pregnancy loss patients. We will keep track of all patients that experience side effects on this medication.

For patients using oral doxycycline there is a small risk of side effects including decreased appetite, nausea, vomiting, diarrhea, allergic reaction and anemia. In our experiences we have found that <1% of our patients have bothersome side effects with oral doxycycline which we routinely use for many of these patients. . We will keep track of all patients that experience side effects on this medication.

Vaginal probiotics is an over the counter supplement that is not expected to have side effects other then difficulty with insertion or change in typical vaginal discharge. None the less we will keep track if any patient reports any bothersome side effect and discontinue its use if there are any.

ii. Person(s) responsible for Data and Safety Monitoring

The protocol director will be monitoring all unanticipated problems and adverse events.

iii. Frequency of DSMB meetings

N/A

iv. Specific triggers or stopping rules

The risk of complications with an endometrial biopsy in the general population is approximately 1%. If we experience a higher complication rate then this we will terminate the procedure.

If any patient reports persistent side effects while on vaginal progesterone this will be stopped for this patient as it would be based on standard of care practice.

v. DSMB Reporting

N/A

vi. Will the Protocol Director be the only monitoring entity? (Y/N)

Yes

vii. Will a board, committee, or safety monitor be responsible for study monitoring? (Y/N)

No

---

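### The written doxycycline stop puts hives under the same try-food-first rule as stomach upset, and no immediate stop for hives or allergic reaction is stated

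*Protocol*

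**What the plan says.** Section 2.a of the protocol prescribes, for women with an altered microbiome, "a 2 week course of oral doxycycline will be prescribed followed by 2 weeks of over the counter vaginal probiotics". The same section classifies this use of antibiotics: "using this in the setting of an abnormal microbiome in combination with over the counter vaginal probiotics would be considered research".

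Section 8.a (iii) lists nausea, decreased appetite, vomiting, diarrhea, hives and anemia as reported symptoms on doxycycline, then gives one rule for the whole list: "diarrhea, hives and anemia. If these symptoms developed and didn't resolve with minimal intervention (taking food with medicine) the treatment would be stopped". The sentence closes by describing this as what the clinic already does.

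Section 8.e (i) gives a similar list, with hives replaced by a broader term: "decreased appetite, nausea, vomiting, diarrhea, allergic reaction and anemia". It adds that "we have found that <1% of our patients have bothersome side effects with oral doxycycline" and that side effects on the drug will be tracked. Section 8.e (iv), which holds the specific triggers and stopping rules, covers biopsy complications and one drug: "If any patient reports persistent side effects while on vaginal progesterone this will be stopped for this patient". For the vaginal probiotic, 8.e (i) says: "None the less we will keep track if any patient reports any bothersome side effect and discontinue its use if there are any".

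**The concern.** Trying the drug with food is a sensible first response to stomach upset. It is not a response to hives, which point to allergy. The rule in 8.a (iii) does not separate the two, so on its plain wording the stop for hives comes after an unsuitable measure has been tried and has failed.

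What is at stake is the safety of individual women, not inference. Section 2.a treats this antibiotic use as research, so for some women the exposure arises from the study. The protocol director is the only monitoring entity (8.e, items vi and vii), which makes it more useful for the written rule to be right without interpretation.

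**Working it through.** This is mainly a comparison of texts, with one piece of arithmetic for scale.

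**1. Does the rule cover hives?** The rule in 8.a (iii) refers back to the symptoms in the sentence before it. There are six, and hives is one of them. Nothing in the wording sets hives apart.

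**2. Does the named intervention fit each symptom?**

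| Symptom in 8.a (iii) | Food step a sensible first response? |
|---|---|
| Nausea | Yes |
| Decreased appetite | Yes |
| Vomiting | Yes |
| Diarrhea | Yes |
| Hives | No: allergic sign |
| Anemia | No: not a stomach symptom, but the stop if it does not resolve is still useful |

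The step fits four of the six. Hives is the symptom for which waiting matters.

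**3. Is an immediate stop stated elsewhere?**

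- 8.e (i): allergic reaction is named as a doxycycline risk; the only action given is tracking.
- 8.e (iv): covers biopsy complications and persistent side effects on progesterone; doxycycline is not mentioned.
- 2.a: gives the course and leaves regimens to the treating physician; it has no stopping rule for doxycycline.
- 7.h: the exclusion criteria name no doxycycline or tetracycline allergy.

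No section states an immediate stop for hives or allergic reaction.

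**4. How does the rule compare with the probiotic's?** Section 8.e (i) discontinues the probiotic for any bothersome side effect, with no intermediate step. The doxycycline rule has an intermediate step, although doxycycline is the only one of the three treatments for which 8.e lists allergic reaction.

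**5. Scale.** Inputs: 100 women with recurrent pregnancy loss and 100 with unexplained infertility (7.a); no planned repeat biopsy in controls (2.g), read here as no study treatment in controls; under 1% with bothersome doxycycline effects (8.e (i)).

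- Ceiling on women treated: 100 + 100 = 200.
- Expected with any bothersome effect: fewer than 200 × 0.01 = 2.
- If controls with an altered microbiome were treated too: ceiling 300, and fewer than 300 × 0.01 = 3.

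If a share *p* of the 200 has an altered microbiome and accepts treatment, the bound becomes 200 × *p* × 0.01. The protocol gives no *p*. It also gives no rate for hives, which is an unknown part of the bothersome effects, so none is computed.

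**The case against.** The strongest reply is that the rule already leads to a stop. If food does nothing for hives, its condition is met and the drug is stopped. The sentence does not say that stopping is allowed only then, and it tells nobody to continue through hives. This stands, and it limits the point to timing.

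A second reply is that the parenthesis is just an illustration, as in the progesterone paragraph just above it, where a headache relieved by a simple analgesic is given. That reading is possible. However, the progesterone paragraph marks its case as an example and the doxycycline sentence does not. Even as an illustration, it leaves the stop for hives dependent on some minimal measure having failed.

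A third reply is clinical discretion: 2.a says "treatment regimens will be determined by the treating physician according to the standard of care", the rule is tied to the clinic's existing practice, side effects are tracked, and women may leave the study at any time (7.i). Clinicians would probably stop at once. But the existing practice that 8.a (iii) describes is the same rule, and the sentence in 2.a concerns standard care, whereas this antibiotic use is classed as research. Neither supplies the missing line.

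A reader of 8.e alone might infer that doxycycline has no written stop at all. That is not supported: 8.a (iii) gives one, and it does not lapse because 8.e does not repeat it. Nor do the documents support an inference that the repeat-biopsy findings are affected.

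**Conclusion.** The point holds as a question of when doxycycline is stopped. The protocol has a stopping rule for the drug, but applies one condition, failure of minimal intervention, to an allergic sign it does not fit, and states no immediate stop for hives or allergic reaction in 8.a or 8.e.

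The expected number of women is small: fewer than 2 of at most 200 with any bothersome effect. This assumes that the clinic's own experience carries over to this study and that controls are not treated. The number with hives is unknown and smaller still. The true exposure is probably below 200, since women may choose observation only (7.a), not every microbiome will be altered, and antibiotics for endometritis are standard care (2.a).

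No endpoint, comparison or sample size is touched. The change is worth making because the event can be serious and the correction costs almost nothing.

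**What to change.** In 8.a (iii), keep the existing stop for the listed symptoms other than hives, including the stop for anemia that does not resolve. Attach the food step to nausea, decreased appetite, vomiting and diarrhea. Then add: *Doxycycline is stopped at once for hives or any sign of allergic reaction.* Repeat that line in 8.e (iv), so that the list of triggers covers the drug. Confining the whole rule to the four gastrointestinal symptoms would be a mistake, because it would remove the written stop that anemia now has.

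The cost is one revised passage in 8.a (iii) and one added line in 8.e (iv). The downside is that a few women may not complete the 2-week course before the second biopsy.

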**b. International Research Risk Procedures**

N/A

---

**c. Procedures to Minimize Risk**

Clinical study staff will explain all procedures thoroughly to consented subjects and why each diagnostic test is being done during their evaluation. There are no anticipated

additional risks to a patient who is involved in this study as compared to a nonparticipating patient in the same clinical setting. Subject identity will be kept confidential.

---

**d. Study Conclusion**

The study will terminate once the desired number of participants has been reached and each patient has been followed for 5 years from the date of enrollment.

---

**e. Data Safety Monitoring Plan (DSMC)**

i. Data and/or events subject to review

Since we will be performing endometrial biopsies in patients enrolled in this study, there is a small risk of bleeding and infection that can occur as result of this intervention (<1%) We will keep track of all patients that experience complications as a result of this procedure.

For patients who use vaginal progesterone there is a small risk of side effects from systemic absorption of the progesterone: Bloating, stomach/abdominal pain, nausea, breast tenderness, headache, drowsiness, mood swings, irritability, or vaginal discomfort. In our experience we have found that <1% of our patients have bothersome side effects with vaginal progesterone which we routinely use for many infertility and recurrent pregnancy loss patients. We will keep track of all patients that experience side effects on this medication.

For patients using oral doxycycline there is a small risk of side effects including decreased appetite, nausea, vomiting, diarrhea, allergic reaction and anemia. In our experiences we have found that <1% of our patients have bothersome side effects with oral doxycycline which we routinely use for many of these patients. . We will keep track of all patients that experience side effects on this medication.

Vaginal probiotics is an over the counter supplement that is not expected to have side effects other then difficulty with insertion or change in typical vaginal discharge. None the less we will keep track if any patient reports any bothersome side effect and discontinue its use if there are any.

ii. Person(s) responsible for Data and Safety Monitoring

The protocol director will be monitoring all unanticipated problems and adverse events.

iii. Frequency of DSMB meetings

N/A

iv. Specific triggers or stopping rules

The risk of complications with an endometrial biopsy in the general population is approximately 1%. If we experience a higher complication rate then this we will terminate the procedure.

If any patient reports persistent side effects while on vaginal progesterone this will be stopped for this patient as it would be based on standard of care practice.

v. DSMB Reporting

N/A

vi. Will the Protocol Director be the only monitoring entity? (Y/N)

Yes

vii. Will a board, committee, or safety monitor be responsible for study monitoring? (Y/N)

No

---

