#### **b. Procedure Risks**

New patients will not be exposed to any additional research procedures outside the standard of care. For return patients they will undergo a simple uterine biopsy that they will have the knowledge ahead of time about as they have already undergone the same procedure previously. For the healthy controls they will undergo one minor procedure any may benefit from the testing in the future. The endometrial biopsy in general is a low risk procedure with a risk of complications of less than 1 in 1,000 with the most common side

effects of short lived (lasting a few minutes at most) of mild cramping and mild spotting

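### The biopsy stopping trigger is set at the very complication rate the monitoring plan expects, and Procedure Risks gives a rate at least ten times lower

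*Protocol*

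**What the plan says.** Three statements in the protocol bear on how often endometrial biopsy leads to complications.

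- Section 2.b (Procedure Risks) gives a "risk of complications of less than 1 in 1,000". It treats as side effects the "effects of short lived (lasting a few minutes at most) of mild cramping and mild spotting".
- Section 8.e.i (events subject to review) refers to a "small risk of bleeding and infection that can occur as result of this intervention (<1" percent). It adds: "We will keep track of all patients that experience complications as a result of this procedure".
- Section 8.e.iv (triggers or stopping rules) says: "The risk of complications with an endometrial biopsy in the general population is approximately 1" percent. The rule follows directly: "If we experience a higher complication rate then this we will terminate the procedure".

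This is the only numerical trigger for the biopsy. Section 8.e gives no number of biopsies before it applies, no times at which the rate is checked, no margin above 1% and no definition of a complication. It does not say whether the rate is per patient or per biopsy. The tracking sentence points to patients, but section 2.a allows repeat biopsies. On oversight, section 8.e.ii says: "The protocol director will be monitoring all unanticipated problems and adverse events".

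**The concern.** There are two linked problems.

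First, two background rates for one procedure differ at least tenfold, and the stopping rule is built on one of them. A reader cannot tell which rate the investigators expect.

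Second, on the rate used in section 8.e.iv, the threshold is the expected rate itself. An observed proportion lies above its own expectation a good part of the time by chance, and repeated checking makes this more likely. The wording commits the team to terminate, so following the rule as written could end the procedure when nothing is wrong. How likely that is depends on a look schedule that the protocol does not give.

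**Working it through.** The protocol gives no error rate for this rule, so there is no figure of its own to reproduce. The check compares the two rates and then computes how the rule behaves.

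**Inputs**
- Rate in section 8.e.iv: about 1% (0.01).
- Rate in section 2.b: below 0.1% (0.001).
- Number of biopsies: up to 300. This is an assumption: three groups of 100 (section 7.a), one first biopsy each. Repeat biopsies would raise it; the observation-only option in section 7.a could lower it.
- Trigger read literally: stop when events/biopsies > 0.01.

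**Step 1: the gap.** 0.01 / 0.001 = 10, so the two rates differ at least tenfold. The bleeding-and-infection figure of under 1% fits either rate and does not settle which is right.

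**Step 2: trigger in counts.** More than 1% means at least 2 events at 100 biopsies (2/100 = 2%), at least 3 at 200 and at least 4 at 300. Before 100 biopsies a single event is enough, since 1/99 = 1.01%.

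**Step 3: single looks at a true 1%.** With X binomial(n, 0.01):
- n = 100: 1 - P(0) - P(1) = 1 - 0.3660 - 0.3697 = 0.264.
- n = 300: 1 - P(0) - P(1) - P(2) - P(3) = 1 - 0.0490 - 0.1486 - 0.2244 - 0.2252 = 0.353.
- At least one event in the first 99: 1 - 0.99^99 = 0.630.

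**Step 4: repeated looks.** An exact binomial recursion carries forward the probability of each event count and removes the paths that have crossed the trigger at each look.

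| True rate | One look at 100 | One look at 300 | Every 100 to 300 | After every biopsy to 300 |
|---|---|---|---|---|
| 0.1% | 0.5% | 0.03% | 0.5% | 10% |
| 0.5% | 9% | 7% | 14% | 47% |
| 1% | 26% | 35% | 47% | 77% |
| 2% | 60% | 85% | 89% | 97% |

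The last column depends most on the literal cutoff. At a true 1%, 63 of its 77 percentage points come from a single event somewhere in the first 99 biopsies.

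**Step 5: a rule with a margin, for illustration.** Stop at 4 or more, 6 or more, and 7 or more events after 100, 200 and 300 biopsies. The same recursion gives an overall chance of stopping of under 0.01% at a true 0.1%, 4.7% at 1%, 43% at 2%, 81% at 3% and 99% at 5%.

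**The case against.** The strongest reply is that the rule works well if section 2.b is right. A 1% trigger over a background of at most 0.1% is then an ordinary safety margin: false stops run from 0.03% (one look at 300) to 10% (after every biopsy), and a true 2% is caught 85% to 97% of the time on those two schedules. This stands. A reader might infer that the trigger is unsound under either rate, being too quick at 1% and too lax at 0.1%. The documents do not support the second half, because the protocol names no rate between 0.1% and 1% as unacceptable. What remains in that case is narrower: the reason given for the trigger, that 1% is the background rate, would be wrong.

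Differing definitions may also explain part of the gap. Section 2.b sets mild spotting aside as a side effect, while section 8.e.i names bleeding as a risk. That is plausible, but no definition is given, so the gap stays open.

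The N/A entered for the frequency of DSMB meetings might be read as saying that no review is planned. It does not say that. It matches the statement that there is no board, and the protocol director monitors adverse events throughout.

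Finally, the stakes are modest. The procedure is low-risk, and for patients the protocol says "currently endometrial biopsy is a standard of care for recurrent pregnancy loss and unexplained infertility". A reader might infer that a false stop would cost the trial its biopsies and data. The protocol does not say which biopsies termination would cover, so that loss cannot be claimed.

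An unseen statistical analysis plan does not answer the point, because the protocol itself fixes the rule.

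**Conclusion.** The concern holds in this form. The protocol gives two background rates that cannot both describe the same event, and sets its only numerical biopsy trigger at the higher one. If that rate is true, the rule trips by chance between 26% and 77% of the time across the schedules computed, depending only on when the rate is checked. If the lower rate is true, false stops are uncommon and the threshold may be acceptable, but not for the reason stated.

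The figures assume up to 300 independent biopsies with a constant risk, and a literal cutoff at 1% although the protocol says approximately. The error at a true 1% is towards stopping, and individual adverse-event monitoring continues whatever the rule does. This should be fixed, at the low end of that category.

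**What to change.** Amend sections 2.b and 8.e in one paragraph:

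1. Reconcile the two complication rates and state one.
2. Say whether the rate is per patient or per biopsy, and that mild cramping and spotting do not count as complications.
3. Restate the trigger as event counts at stated looks, with a margin above the reconciled rate.

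The boundary in step 5 of the working is one example, suited to a reconciled rate of 1%. No particular boundary is required, and a lower reconciled rate would call for lower counts.

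The cost is a slower reaction to a moderate excess. At a true 2% the example stops 43% of the time, against 89% for the present rule on the same three looks. The protocol director's adverse-event monitoring continues alongside and can act sooner. A review after any serious complication could be added, but that is a preference and not needed to correct the rule.
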